1. BACKGROUND

Shoulder pain is highly prevalent, being the third main complaint in primary care settings.^{1–3} There is a wide range of reported incidence and prevalence rates, with a median of 24.8% of adults reporting shoulder pain every month.⁴ In developed countries, 1% of adults annually consult a primary care provider due to shoulder pain.^{2,5}

Around 65 to 70% of shoulder pain complaints involve problems in the rotator cuff (RTC) tendons,^{1,6} with incidence rising higher after the 4th decade of life.^{1,7–9} Abundant data from across the world is available on the prevalence of RTC pathologies.^{6,10–16}

RTC dysfunction represent a huge burden for healthcare systems, insurance companies and employers alike.^{1,17} Shoulder problems account for 2.4% of all general practitioner consultations in the UK,¹⁸ and 4.5 million visits to physicians annually in the USA.¹⁹ One study in the UK²⁰ estimated that nearly £310 million is spent on medical appointments in the first 6 months of shoulder pain onset, and additional costs of surgical procedures are estimated at approximately £30 million/year, with up to 50% of these costs related to sick leave from paid employment. More than 300,000 surgical repairs for RTC pathologies are performed annually in the USA, and the annual financial burden of RTC management was also estimated at \$3 billion.²¹

A myriad of international clinical practice guidelines have been put forth over the years, outlining the management of pain-causing shoulder disorders.^{22–26} Most causes of mild-to-moderate and gradual onset shoulder pain are treated initially with conservative care. Indeed, many recent studies and systematic reviews, as well as the American Academy of Orthopaedic Surgeons guidelines, support that firstly the patient should be directed to a physical therapy (PT) program and not surgery. ^{26–30} For some specific conditions (e.g., symptomatic small to medium full-thickness RTC tears), strong evidence further supports that both PT and operative treatment attain significant improvements in patient-reported outcomes.²⁶ Of note, another systematic review on treatment options for shoulder pain suggests that passive modalities, such as manual therapy, electrotherapy and taping should be avoided as mono-therapy but that they could, in specific cases, provide

additional benefit when utilized in conjunction with therapeutic exercise programs.³¹ This suggests that the exercise component of PT is fundamental in the treatment of painful shoulder disorders.

Regarding rehabilitation setting, some studies show that home-based therapy, based on exercise, could be as effective as conventional PT interventions.^{32,33} This is in line with the recent trends in healthcare delivery, moving away from inpatient care and towards home-based care with the intent of improving cost-effectiveness. Furthermore, the need for home-based digital solutions is now felt more acutely than ever, in the face of the current pandemic.^{34–36} In this context, solutions enabling home-based rehabilitation without requiring real-time human supervision can be key to improving effectiveness and lowering costs, while keeping all stakeholders safe. Indeed, there are studies demonstrating the potential^{37–39} and cost-effectiveness⁴⁰ of shoulder postoperative care and rehabilitation through telehealth solutions.

However, while evidence is growing that digital therapeutics (DTx) can improve outcomes, personalize care and decrease costs,⁴¹ there is still much ground to be explored in the field of digital therapy following RCR.^{42,43} Several studies can be found on the validation/development of systems/algorithms for monitoring shoulder motion to assist clinicians on patient evaluation^{44,45} but these do not meet the aforementioned needs and cannot be considered digital therapeutics.

There have been some advances on new technologies for shoulder rehabilitation, namely using wearable sensors⁴³ and augmented reality.⁴⁶ Of note, some of these studies focus on systems based on inertial motion trackers that can be used by the patient at home, under remote monitoring from the physical therapist. However, these are either in very preliminary stages of development or validation,^{47–51} with no clinical validation studies performed, or are directed at rehabilitation after stroke.^{43,46}

SWORD Health has developed a novel motion tracking-based digital biofeedback system for home-based physical rehabilitation - SWORD Phoenix[®]- which is an FDA-listed class II medical device. The company has previously conducted two pilot studies (NCT03047252; NCT03045549) comparing a digital therapy program using this device against conventional face-to-face physical therapy. These studies have proven the feasibility, safety and effectiveness of this digital therapeutic on rehabilitation after total knee and hip arthroplasty.^{52–54}

This is a single-center, prospective, randomised, controlled study, with two parallel groups, designed to assess the clinical impact of a digital exercise program against conventional rehabilitation for shoulder tendonitis. The hypothesis is that all the clinical outcomes measured

will significantly improve after the program, and patients using this novel system will attain at least the same outcomes than the ones attained by the conventional PT group.

2. SWORD HEALTH DIGITAL CARE PROGRAMS

SWORD Health's Digital Care programs address the three pillars of musculoskeletal care: therapeutic exercise, patient education and cognitive behavioural therapy (CBT).

The exercise component is delivered through a digital feedback system - SWORD Phoenix[®]which is an FDA-listed class II medical device. This device uses motion tracking technology to digitize motion and provide real-time biofeedback on performance during exercise execution (see more below). This allows individuals to perform independent exercise sessions at home without the need for constant face-to-face therapist supervision, while still being remotely monitored (asynchronously) through a cloud-based Portal.

The safety and effectiveness of digital exercise programs performed with this device, in a homebased scenario, have already been demonstrated for recovery after total knee and hip arthroplasty.^{53–55} In these studies, where digital programs based on this device were compared with conventional PT, the clinical outcomes were superior in the digital group. These results were explained by (a) the positive impact of a kinematic biofeedback tool on patient performance, especially regarding error correction and stimulation of a greater range of motion; (b) patient empowerment regarding their rehabilitation process; (c) high patient engagement through the use of gamification strategies; (d) the positive effect of remote monitoring on patient effort and (e) the availability of objective data for clinical review, enabling data-driven decisions.

The education component is delivered through a smartphone app. Through this app, each individual is presented with educational content on their condition, in the form of small articles curated by SWORD's clinical team, focusing on subjects ranging from anatomy and physiology, pain, exercise and fear avoidant behaviours.

The CBT component takes the form of an 8-week program based on third-generation CBT techniques, particularly Mindfulness Based Stress Reduction, Acceptance and Commitment

Therapy and Compassion-based therapy. The program is presented to individuals through email, with links to short, pre-recorded, self-guided, meditation sessions, as well as written mindfulness exercises called "habit releasers".

3. System technical specifications

SWORD Phoenix® is a proprietary, 510(K) exempt, class I medical device, with CE mark, which is composed of the following three interconnected components:

- Motion trackers, placed on body segments using Velcro[®] straps. Each motion tracker is placed in a specific position. To assist in the correct placement of the motion trackers, both the trackers and the matching straps are color-coded. The motion trackers' setup varies according to each therapy.
- Mobile App, that comes pre-installed on a tablet, that guides the patient in each exercise session. Before each exercise, the patient is presented with a real-life video and audio explanation of that exercise. The execution interface is subsequently shown. This screen features: a) a progress bar; b) a repetition counter; c) a star counter and d) a timer displaying time left in the exercise. A correct repetition is defined as a movement starting at the baseline and reaching or surpassing the specified target, without violating movement or posture constraints. In case the patient violates a constraint, a message is prompted showing which movement error was performed, so that the patient can correct the movement in the following attempts. For each correct repetition, the patient earns from 1 to 5 stars, depending on the range of motion of that specific movement in comparison to normative values for that movement. At the end of each session, the patient is presented with a summary of the number of completed repetitions and stars, as well as with badges rewarding him for the progresses achieved in each exercise.
- Web-based Portal that allows the clinical team to generate new patient profiles and create exercise sessions for each patient. To prescribe a session, the clinician needs to select the exercises, number of sets and number of repetitions. When a patient performs a session, the results are uploaded to the platform and available for review. Based on this information, the clinical team can edit the parameters of each exercise according to patient performance and progress.

4. SECURITY AND DATA STORAGE

4.1 DATABASE

The networks where SWORD Health's infrastructure is hosted are maintained by Google and are included in Google Cloud Platform's SOC2 and HITRUST certifications. Security-related configurations are registered and verified periodically.

Collected data is stored in databases that are only accessible to SWORD's Application Programming Interface (API), and Personal Health Information (PHI) is individually encrypted inside this database. Separate databases are used for development, QA, and production environments.

4.2 WEB PORTAL

Data is secured in transit to SWORD's Application Programming Interface (APIs) due to enforced application of TLS 1.2 or above. Additionally, a web application firewall protects our servers from Cross-site Scripting (XSS) and SQL Injection attacks.

Access to SWORD's Web Portal is provided only to individuals who have a valid work contract with SWORD Health and have a role within the company that allows them to use the platform (i.e. PTs and IT support).

Access control mechanisms ensure that only authorized users have access to PHI and different functions are mapped to different roles within the platform (i.e. IT support personnel only have access to de-identified data).

4.3 WEBSITE

SWORD's Onboarding Website does not have a login function as it works only as a registry platform and user accounts are created in SWORD's Web Portal. Data is secured in transit to SWORD's Application Programming Interface (APIs) due to enforced application of TLS 1.2 or above. Additionally, a web application firewall protects our servers from Cross-site Scripting (XSS) and SQL Injection attacks.

4.4 MOBILE APP

For an individual to access the mobile app in the medical device, their profile must be created in SWORD's Web Portal. Upon profile creation, the individual is attributed a unique QR card that is shipped together with the medical device kit. Upon the first usage, the individual is required to set a personal pin code (two-factor authentication is employed, as the user must scan their QR code and input a confirmation code sent by text message. This is required for the first login, with subsequent logins being done by presenting the pin and the QR card. Each session expires within 24 hours, requiring the individual to present these again if >24 hours have passed since the last usage.

Transport Layer Security (TLS) protocols are applied on every connection to ensure secure data transmission between the mobile app and the Database. Additionally, data stored in the device is also encrypted.

5. STUDY OBJECTIVE

To assess the clinical outcomes of a digital program for chronic shoulder tendonitis versus conventional. PT.

6. STUDY HYPOTHESIS

The digital program will be associated with at least the same outcomes as conventional PT.

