9. SAMPLE SIZE ESTIMATION

Sample size estimation calculations were performed taking into consideration the primary outcome measure – the QuickDASH. In a sample of 57 patients with shoulder tendon disorders treated with SWORD Health's medical device in the context of work-related conditions, the mean and standard deviation of the QuickDASH scale at baseline was of 59 and 19 points respectively. A Minimal Detectable Difference (MDD) of 11.2 points was considered, based on the psychometric properties of the scale.⁵⁶ Considering a power of 80%, a two-sided 0.05 significance level and a 10% dropout rate, 80 (40+40) patients would be necessary to detect a 11.2 points difference between the two groups.

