16. STATISTICAL ANALYSIS PLAN

To assess differences in clinical and demographic variables of the patients allocated to the two study groups, independent samples t test or Mann–Whitney U test will be used for quantitative variables. For categorical variables, Chi-square test or Fisher's exact test will be used. Outcome analysis will be performed using both an intention to treat analysis and a per-protocol analysis.

The overall impact of the intervention on the primary and secondary outcomes will be assessed considering both the results at the 8-week assessment as well as change from baseline.

Differences between interventions will be evaluated using independent samples t test or Mann-Whitney U test. For non-normally distributed variables, the magnitude of the difference in the medians will be assessed using Hodges-Lehman estimator. Additionally, a repeated measures ANOVA will also be performed, with group as an independent factor and time as a within-subjects factor. When necessary, logarithmic transformation will be performed to obtain normally distributed variables. In all analysis, a significant level of 0.05 will be considered.

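### The hypothesis is that digital is at least as good as conventional PT, but the plan has only no-difference tests and no margin or decision rule, so only significant superiority could validly support it

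*Combined protocol and SAP*

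**What the plan says.** The between-group hypothesis appears twice. Section 6 reads "The digital program will be associated with at least the same outcomes as conventional PT", and the end of section 1 predicts that "patients using this novel system will attain at least the same outcomes than the ones attained by the conventional PT group". The objective in section 5 is neutral ("To assess the clinical outcomes of a digital program for chronic shoulder tendonitis versus conventional" PT), and the design is nowhere labelled non-inferiority or equivalence.

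Section 9 bases the sample size on detecting a difference. It states "A Minimal Detectable Difference (MDD) of 11.2 points was considered, based on the psychometric properties of the scale", takes 80% power, a two-sided 0.05 level and 10% dropout, and concludes that 80 (40+40) "patients would be necessary to detect a 11.2 points difference between the two groups".

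Section 16 says "Differences between interventions will be evaluated using independent samples t test or Mann-Whitney U test" and adds a repeated measures ANOVA, all at 0.05. For non-normal variables only, "the magnitude of the difference in the medians will be assessed using Hodges-Lehman estimator"; no interval or margin goes with it. Both the 8-week value and the change from baseline are to be considered. On analysis sets, "Outcome analysis will be performed using both an intention to treat analysis and a per-protocol analysis", with neither named as deciding.

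**The concern.** A claim that a new treatment is at least as good as a comparator is supported when the data exclude a deficit larger than some stated amount. The t test, the Mann-Whitney test and the group comparison in the ANOVA ask whether the arms differ. Failing to reject that null does not show that digital is not worse. The plan therefore has a hypothesis and a set of tests with nothing to connect them.

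Two things are at stake. If digital and conventional PT really perform alike, the trial has almost no valid way of saying so. And because no decision rule exists, a non-significant result could later be presented as confirming the hypothesis. In a trial of this size that could easily happen when digital is materially worse.

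**Working it through.** **Inputs.** From section 9: SD 19 (baseline QuickDASH in 57 earlier patients), difference 11.2, two-sided 0.05, power 80%, dropout 10%, 40 per arm. Evaluable per arm: 40 × 0.9 = 36. SD 19 is assumed to apply to the 8-week comparison; the documents give no SD at 8 weeks or for change.

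**The plan's own figure.** With the normal approximation, n per arm = 2 × (1.960 + 0.842)² × 19² / 11.2² = 45.2, so 46. After dropout, 46 / 0.9 = 51.1, so 52 per arm and 104 in total. The stated 80 is not reproduced. It does follow from a one-sided 0.05 level: 2 × (1.645 + 0.842)² × 19² / 11.2² = 35.6, so 36, and 36 / 0.9 = 40 per arm. Section 9 says two-sided. This shortfall is a separate matter, but it affects some figures below.

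**Precision.** SE = 19 × √(2/36) = 4.478. With t(0.975, 70 df) = 1.994, the expected 95% CI half-width is 1.994 × 4.478 = 8.93 points.

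**Arms truly equal.** The probability of a significant result favouring digital is half of 0.05, that is 2.5%.

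**If p > 0.05 were read as support.** P(not significant) comes from the noncentral t distribution with 70 df and noncentrality (true deficit) / SE.

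| True deficit of digital | SD | Noncentrality | P(p > 0.05) |
|---|---|---|---|
| 11.2 | 19 | 2.50 | 31% |
| 8 (illustrative) | 19 | 1.79 | 58% |
| 5.6 (illustrative) | 19 | 1.25 | 77% |
| 11.2 | 15 (assumed) | 3.17 | 12% |
| 11.2 | 23 (assumed) | 2.07 | 47% |

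If the stated 80% power held, the figure at 11.2 would be 100% − 80% = 20%.

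**Power of a non-inferiority rule at the planned N.** Power is the probability that the two-sided 95% CI excludes the margin, with true difference 0 and SD 19. The documents give no margin, so both margins are assumptions.

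| Margin | Evaluable per arm | Baseline adjustment | Power |
|---|---|---|---|
| 11.2 | 36 | none | 69% |
| 8 | 36 | none | 42% |
| 11.2 | 36 | correlation 0.3 | 73% |
| 11.2 | 36 | correlation 0.6 | 87% |
| 11.2 | 30 (assumed per-protocol set) | none | 61% |
| 11.2 | 25 (assumed per-protocol set) | none | 53% |

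Adjusted rows use residual SD 19 × √(1 − r²), which is 18.1 at r = 0.3 and 15.2 at r = 0.6, with 69 df. Unadjusted at margin 11.2 and 36 per arm, power is 88% at SD 15 and 53% at SD 23.

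**Size needed for 80% non-inferiority power.** Enrolled = 2 × (n / 0.9, rounded up). The lower figure of each unadjusted pair uses the normal approximation, the higher the t distribution.

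| Margin | Adjustment | n per arm | Enrolled |
|---|---|---|---|
| 11.2 | none | 46–47 | 104–106 |
| 11.2 | correlation 0.3 | 43 | 96 |
| 11.2 | correlation 0.6 | 30 | 68 |
| 8 | none | 89–90 | 198–200 |

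**The case against.** The strongest reply is that the hypothesis is an informal expectation and the real design is an ordinary two-sided comparison. The objective is neutral, nothing is labelled non-inferiority, the plan never says a non-significant p-value will count as support, and section 13 gives the analysis to an independent statistician. It is true that the error rates for reading p > 0.05 as support depend on a reading the plan does not state. But the hypothesis has its own numbered section and is repeated in section 1, and an independent analyst is not a decision rule. The 2.5% figure needs no misreading.

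A second reply is that 11.2 points is an implicit margin, since N = 80 matches a one-sided 0.05 calculation at that value. Section 9 calls it a detectable difference and ties it to a two-sided test, so it cannot be read as a margin. The sponsor should be asked whether a one-sided calculation was meant.

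A third reply is partly right: the 31%, the 69% power and the enrolment of 104–106 partly reflect the separate sample-size shortfall. At 47 evaluable per arm the 31% would be 19%, and the stated two-sided inputs alone already require about 104 enrolled. Not all of that extra enrolment is due to the missing margin.

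Finally, the Hodges-Lehmann estimate and the ANOVA do not close the gap. The first has no stated interval and covers non-normal variables only. The time factor of the second can address improvement within groups, not the comparison between them.

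**Conclusion.** The concern holds and must be resolved before outcome data are seen, because it governs the main conclusion on the primary outcome. The absence of a margin, an interval rule or a confirming result is a matter of text and depends on no assumption. Nor does the 2.5% chance of valid support under true equality depend on the SD.

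The risk of a false claim is conditional on p > 0.05 being read as support. At a true deficit of 11.2 points, the only threshold in the documents, it is 31% at SD 19 with 36 per arm, 12% to 47% over SD 15 to 23, and 20% if the stated power held. The SD changes these sizes but supplies no decision rule.

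**What to change.** Take one of two equally acceptable routes before data are seen.

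**Route A: keep the not-worse claim.**
- Pre-state a non-inferiority margin for the QuickDASH difference and justify it clinically. The 11.2 points is a psychometric detectable difference and is not by itself an acceptable loss.
- State that the confirmatory claim concerns QuickDASH, since section 6 refers to outcomes in general.
- Name one primary analysis: 8-week value or change, adjusted for baseline or not.
- Conclude at least the same only if the two-sided 95% CI excludes the margin on the digital-worse side. Test superiority only after that.
- State the roles of the intention-to-treat and per-protocol analyses, and restate the power at the planned N.

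The cost is the wording, the margin justification, and either a lower stated power at N = 80 or a larger N as tabulated. If a smaller per-protocol set must also succeed, power falls further. The claim becomes harder to make.

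**Route B: drop the not-worse claim.** Reword sections 1 and 6 as a test or estimate of the between-group difference, report that difference with its 95% CI, and state that p > 0.05 will not be read as showing at least the same outcomes. The cost is the rewording and one reporting sentence, at the same N.

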7. STUDY DESIGN

Prospective, single-center, parallel-group, randomised controlled study.

8. STUDY OUTCOMES

8.1 Primary Outcome

Impact on physical function and symptoms measured through the shortened Disabilities of the Arm, Shoulder and Hand questionnaire (QuickDASH) between baseline and 8 weeks.

8.2 Secondary Outcomes

The secondary outcomes will include the following:

a) Impact on shoulder range of motion

Shoulder range of motion will be measured in the following exercises: shoulder flexion; shoulder abduction and external shoulder rotation at 90 degrees of abduction.

b) Impact on Pain

Measured through the following question: "On a scale of 0 to 10, where 0 is no pain and 10 the worst pain imaginable, how would you rate your pain in the last 24 hours?"

c) Interest in undergoing surgery

Measured through the following question: "On a scale of 0 to 10, where 0 is not at all and 10 is extremely interested, how interested are you in undergoing shoulder surgery in the next 12 months"?

d) Medication consumption

Measured through the following questions:

- i. "Are you taking any medication for your shoulder pain?";
- ii. "If yes, on how many days in a week, on average, are you taking medication for your shoulder pain"

e) Impact on fear avoidance beliefs

Measured by: Patient-reported questionnaire (Fear Avoidance Beliefs Questionnaire- FABQ)

f) Impact on anxiety and depression

Measured by the General Anxiety Disorder-7 scale and Patient Health Questionnaire-9 scale

g) Impact on work productivity and activity impairment

Measured through Work Productivity and Activity Impairment Questionnaire: Specific Health Problem v2.0 (WPAI:SHP)

h) Satisfaction with social roles and discretional social activities

Measured through the Patient Reported Outcomes Measurement Information System Computerized Adaptive Test (PROMIS-CAT) scales: Ability to participate in social roles and activities (version 2.0) and satisfaction with social roles and activities (version 2.0).

i) Patient engagement

Measured through: g.1) adherence to exercise sessions; g.2) drop-out rates; g.3) treatment intensity (i.e. total number of exercise minutes)

j) Patient satisfaction

Measured through the Net Promoter Score, by asking participants the following question: "On a scale from 0 to 10, how likely are you to recommend this program to a friend or colleague?"

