10. INCLUSION/EXCLUSION CRITERIA

a. Inclusion Criteria

- a) Subjects aged between 18 and 80 years of age at enrolment
- b) Reporting intermittent or persistent shoulder pain for at least 6 weeks, and/or present at least 50% of the time in the past 6 months
- c) Lack of visual/audio or cognitive impairment interfering with the ability to understand or comply with the program

b. Exclusion Criteria

- a) Non-English speaking
- b) Residing outside greater SF area
- c) Known pregnancy
- d) Submitted to spinal surgery less than 3 months ago
- e) Symptoms and/or signs indicative of possible infectious disorder
- f) Referred pain from spine and/or thoracic outlet syndrome
- g) Active cancer diagnosis or undergoing treatment for cancer
- h) Cardiac, respiratory or other known disorder incompatible with at least 20 minutes of light to moderate physical activity
- i) Concomitant neurological disorder (e.g. stroke, multiple sclerosis, Parkinson's disease)
- j) Dementia or psychiatric disorders precluding patient from complying with a home-based exercise program
- k) Illiteracy and/or serious visual or auditory impairment interfering with communication or compliance

Additionally, any patient undergoing a PT program for shoulder pain will be required to stop ongoing programs to enroll in the study.

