15. PARTICIPANT ASSESSMENTS

Patients will be assessed at baseline, 4 and 8 weeks.

Baseline Assessment

This assessment will involve a face-to-face visit, where the following information will be collected:

- a) date of birth
- b) gender
- c) height & weight
- d) body mass index
- e) formal education (years of schooling)
- f) job type
- g) previous shoulder surgery (> 3 months ago)
- h) Working status
- i) Geocodes/zip
- j) Race/ethnicity
- k) Age

The following outcomes will also be assessed in this visit: a) Shoulder Range of Motion; b) PROMIS CAT measures.

Shoulder Range of Motion will be measured in the following movements: 1) shoulder flexion; 2) shoulder abduction; 3) external rotations with shoulder abducted at 90 degrees. The participant will be asked to perform three non-painful repetitions of each movement, in a standing position. The investigator will measure the maximum joint angle attained by the participant, using a digital goniometer in each repetitions. The highest of the three values will be considered.

Regarding satisfaction with social role and ability to participate in social roles and activities, these will be collected through PROMIS CAT v2.0. These will be collected onsite, and the results will then be transferred by the investigator to the eCRF.

Assessment of primary outcome, as well as the remaining secondary outcomes will be performed through an electronic questionnaire to be filled by participants, through the EDC system. These will need to be filled within 5 consecutive days, counting from the date they are sent to the participant. To promote compliance with this schedule, whenever the deadline is approaching, automatic email reminders will be sent to participants. Participants will be excluded from the study

for protocol breach in case they don't fill in the assessment forms. Upon completion of the baseline form, participants in the study will receive a stipend of \$25.

Additional measurements of upper limb function and tri-dimensional motion will also be performed at the onsite visit by the clinician, using a motion capture system. These will not be considered in the outcomes of this study, but will be made available for post-hoc analysis.

Interim assessment (4 weeks)

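### The secondary pain item does not name the shoulder, so pain elsewhere may enter the score; a low-severity wording fix

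*Combined protocol and SAP*

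**What the plan says.** Section 8.2, Secondary Outcomes, lists the outcome under "b) Impact on Pain" and prints the item in full: a 0–10 scale with the question "how would you rate your pain in the last 24 hours". Neither heading nor item gives a body site.

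The next two custom items in the same list do. Item (c) asks "how interested are you in undergoing shoulder surgery in the next 12 months", and item (d) asks "Are you taking any medication for your shoulder pain" and then repeats the shoulder in its follow-up question.

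Section 10 requires shoulder pain for entry: "Reporting intermittent or persistent shoulder pain for at least 6 weeks, and/or present at least 50% of the time in the past 6 months". It admits "Subjects aged between 18 and 80 years of age at enrolment". Its only exclusion aimed at pain from another source is "Referred pain from spine and/or thoracic outlet syndrome".

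Section 15 says that the primary outcome and the secondary outcomes not taken at a visit "will be performed through an electronic questionnaire to be filled by participants, through the EDC system". Only range of motion and the PROMIS measures (plus satisfaction at 8 weeks) are collected face to face, so the pain item is self-completed at baseline, 4 and 8 weeks. No instruction about body site is described.

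**The concern.** The printed wording is the instrument itself, so what it leaves out matters. A participant with a painful shoulder and a painful knee can properly answer for the shoulder, the knee, or whichever is worse. Someone who notices that the medication and surgery items say shoulder, and this one does not, may take it to be broader on purpose.

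Eligibility does not close the gap. Pain referred from the spine is excluded, but independent back, neck, hip or knee pain is not. The baseline data listed in section 15 do not record pain at other sites, so affected answers could not be identified or adjusted for later.

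At stake is how well one secondary outcome measures the condition under trial. Pain elsewhere would add variance and could pull the between-arm difference in shoulder pain away from its true value.

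**Working it through.** **1. Is there a figure in the plan to reproduce?** No. The documents give no SD, expected effect or power for the pain item, no frequency of other-site pain, and nothing on how participants will read the question. Section 9 sizes the trial on QuickDASH alone. Everything numerical below is illustration under stated assumptions.

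**2. Two constructed records, scored as the worse of two pains.**
- Patient A: shoulder 6 then 1; unrelated knee pain 5 at both visits. Scores: max(6, 5) = 6, then max(1, 5) = 5. Recorded change −1; shoulder change −5.
- Patient B: shoulder 4 then 2; new back pain of 6 at week 8. Scores: 4, then max(2, 6) = 6. Recorded change +2; shoulder change −2.

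These show what the wording permits, not how often it would happen.

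**3. Attenuation under a worse-of-two rule.** Assumptions: shoulder pain mean 5.5 and SD 2 at baseline; true falls of 2 and 3 points in the two arms; other-site pain mean 3 to 5 and SD 2, unchanged by treatment; scores rounded and limited to 0–10; every affected patient reports the worse pain. Simulated with 2,000,000 patients per arm. The true week-8 difference is 0.93 rather than 1 because of the rounding and limits.

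| Share with other-site pain | Shrinkage of the difference (other-site mean 3 to 5) |
|---|---|
| 10% | about 5–7% |
| 30% | about 14–22% |
| 50% | about 23–37% |

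At 30% and other-site mean 5, the difference falls from 0.93 to 0.72: (0.93 − 0.72)/0.93 = 0.23, or 22% before rounding.

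The mean score is a mixture of affected and unaffected patients, so shrinkage is proportional to the affected share p: shrinkage = p × k. The table gives k of about 0.47 (23.4%/0.5) to 0.74 (37.2%/0.5). Randomisation makes the expected baseline difference zero, so the expected shrinkage is the same for change from baseline.

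**4. Relaxing the assumptions, at 30% prevalence.**
- Only a quarter of affected patients answer for the worse pain: the effective share is 0.30 × 0.25 = 0.075. Shrinkage is about 0.075 × 0.47 = 3.5% to 0.075 × 0.74 = 5.6% (simulated: 3.5–5.7%).
- Other-site pain falls equally in both arms: by 0.5 points, 12–21%; by 1 point, 10–18%.
- Other-site pain falls 0.5 points more in the arm with the larger shoulder benefit: 5.5–9.5%.
- It falls 1 point more in that arm: about −2%, so the shrinkage is gone and slightly reversed.
- It falls more in the other arm: the distortion grows instead.

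If nobody lets other pain into the answer, there is no effect.

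**5. Noise alone.** Take 40 × 0.9 = 36 evaluable per arm and a two-sided 0.05 t test. A standardised difference of about 0.67 then gives 80% power. If other pain only inflates the variance by a factor r, the standardised difference becomes 0.67/√r. Power falls to about 76% (r = 1.10), 71% (r = 1.25) or 63% (r = 1.50). The documents support no particular r.

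**The case against.** The best defence is context. Participants are identified through physical therapy appointments, enrolled for shoulder pain, and answer this item in the same electronic form as items that say shoulder. Many may rate the shoulder anyway. The outcome is also headed as pain rather than shoulder pain, and other secondary outcomes (anxiety, depression, social roles) are not specific to the shoulder, so the intended meaning is an inference. This stands as a limit on the consequence. It does not remove the ambiguity, because nothing in the plan settles how the question will be read.

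Two stronger readings are tempting, and the documents support neither.

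*That the effect on shoulder pain is diluted, by a known amount.* This needs participants to rate other pain and treatment to leave that pain unchanged. Sections 2 and 14 give the digital arm an 8-week CBT programme and pain education. Annex 3 allows CBT, pain education and work on adjacent joints in the conventional arm. Other-site pain could respond, and unequally, so the direction is not fixed. The 14–22% range sets both assumptions at their unfavourable end.

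*That the wording favours the trial's hypothesis of outcomes at least as good as conventional PT.* Attenuation needs a true difference. It would help that conclusion only if the digital arm were truly worse; if it were better, as the sponsor reports for its earlier studies, attenuation would work against it. Section 16 plans tests of difference and gives no non-inferiority margin for pain. Randomisation also balances other-site pain in expectation at entry, so its mere presence at entry does not favour an arm.

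**Conclusion.** The wording gap is real and nothing else in the documents repairs it: the item names no site, its neighbours do, co-existing pain is admitted, and no instruction limits the answer. The supportable conclusion is that non-shoulder pain may enter the score, adding noise and possibly attenuating or otherwise distorting the comparison of shoulder pain.

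Neither size nor direction can be determined from the documents. The largest figures shown depend on assumed prevalence and pain levels, on worse-of-two reporting by every affected patient, and on no treatment effect at other sites. The effect could be a few per cent or nil.

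This is one secondary outcome among ten. QuickDASH and the sample size are unaffected, and no stated figure changes. It is a low-severity improvement, worth making because it costs so little.

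**What to change.** In 8.2(b), and in the EDC form at baseline, 4 and 8 weeks, insert the word *shoulder* before *pain* in the question, so that it matches items (c) and (d).

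If some participants have already answered the unspecified item, keep one wording within each participant where possible, so that change from baseline compares like with like. Record which wording each participant answered, and describe results from the unspecified wording as overall pain.

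Cost: one word in the protocol and the questionnaire, and a minor IRB amendment. No added patients, visits or items. The downside, if recruitment has begun, is possible mixed wording in early records.
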